8.0 Reportable Events

All contact with the participant will be documented beginning at the consent process through completion of the study. All documentation will be reviewed regularly. Any events that might indicate increased participant distress or anxiety will be promptly brought to the attention of the PI and reported to the IRB and DSMC per reporting guidelines listed below. We will promptly report to the IRB any instances of consent withdrawal due to distress or anxiety. The IRB will be informed at least annually of our data and safety monitoring, summary of participant status, and any changes in the risk of the study.

Reporting to the IRB:

1. Unanticipated problems involving risks to subjects or others will be reported **promptly** to the IRB if they:

- are unexpected;
- are related or possibly related to participation in the research; and
- suggest that the research places subjects or others at a greater risk of harm than was previously known or recognized.

If the serious adverse event does not meet all three (3) criteria listed above, the event does not have to be promptly reported to the Indiana University IRB. However, it should be reported at the time of continuing review.

2. **Prompt** reporting of unanticipated problems to the IRB is defined as within 5 days from becoming aware of the event. AEs will be monitored from the time of consent until the person's participation in the study has ended.

Reporting to the IUSCC Data Safety Monitoring Committee:

Regardless of study sponsorship, the study team must enter all initial and follow-up SAE, expedited, and noncompliance reports into OnCore® for review by the DSMC chair and/or coordinator. Expedited reports may include IRB Prompt Report Forms and additional SAE forms as required by the sponsor. When follow-up information is received, a follow-up report should also be created in OnCore®. This DSMC reporting requirement is **in addition to any other** regulatory bodies to be notified (i.e. IRB, etc.). The DSMC chair and/or coordinator will review all SAE, expedited, and noncompliance reports monthly.

9.0 Data Safety Monitoring

This study will be conducted in accordance with the IU Simon Cancer Center Institutional DSMP for **Low Risk Trials**.

Investigators will conduct continuous review of data and subject safety. **Quarterly review meetings** for low risk trials are required and will include the principal investigator, clinical research specialist and/or research nurse (other members per principal investigator's

discretion). **Quarterly** meeting summaries should include review of data, the number of subjects, significant toxicities as described in the protocol, and responses observed. Study teams should maintain meeting minutes and attendance for submission to the DSMC upon request.

Data and Safety Monitoring Committee

The IUSCC Data and Safety Monitoring Committee (DSMC) is responsible for oversight of subject safety, regulatory compliance, and data integrity for this trial. The DSMC will review this study annually to review overall trial progress, toxicity, compliance, data integrity, and accrual per the Institutional DSMP.

Furthermore, the DSMC conducts an administrative review of serious adverse events (SAEs), deviations, reportable events, and any other outstanding business. Major issues may require further DSMC review or action.

At any time during the conduct of the trial, if it is the opinion of the investigators that the risks (or benefits) to the subject warrant early closure of the study, the DSMC Chair and Compliance Officer must be notified within 1 business day via email, and the IRB must be notified within 5 business days. Alternatively, the DSMC may initiate suspension or early closure of the study based on its review.

Study Auditing and Monitoring

All trials conducted at the IUSCC are subject to auditing and/or monitoring per the Institutional DSMP. Reports will be reviewed by the full DSMC at the time of study review.

Data Management/Oncore Reporting Requirements

The DSMC reviews data and study progress directly from Oncore; therefore, timely data entry and status updates are vital. Study data must be entered within Oncore promptly, no later than one week from study visit occurrence. Subject status in Oncore will be updated in real time, as this may affect overall trial enrollment status. Global SAEs and deviations will be reviewed on a monthly basis by the DSMC Chair directly from Oncore.

Study Accrual Oversight

Accrual data will be entered into the IU Simon Cancer Center OnCore system. The Protocol Progress Committee (PPC) reviews study accrual twice per year, while the PPC coordinator reviews accrual quarterly.

Oncore Safety Reporting

In addition to protocol- and regulatory-required safety reporting, all serious adverse events (SAEs) will be captured in the Oncore system within 1 business day of notification. Initial SAE reporting will include as much detail as available, with follow-up to provide complete information. Attributions will be assessed to study drugs, procedures, study disease, and other alternate etiology.

Protocol Deviation Reporting

Protocol deviations will be entered into OnCore within 5 days of discovery and reviewed by the DSMC Chair on a monthly basis. Findings will be reported to the full DSMC at the time of study review.

10.0 Study Withdrawal/Discontinuation

Criteria for removal from the study are as follows:

- Observed severe cognitive impairment that renders continued participation in the study impossible, such as confusion or impaired ability to read or to provide accurate answers to the interviewer.
- The patient consents to participate in the study, but their family caregiver declines study participation or is not eligible for this study. The patient would no longer be eligible to participate in this study, as we are interested in examining data from patient-caregiver dyads.
- If the patient or caregiver is no longer able to participate in this study due to death or medical factors or decides to stop participation, then the other member of the dyad (patient or caregiver) will no longer be eligible to participate in this study.
- The participant expresses significant distress related to completion of the study (the PI will refer the participant to clinical services if needed).
- The participant provides verbal or written notification that she has decided to discontinue study participation.
- The participant does not follow the study rules (e.g., repeatedly does not answer the phone to complete a scheduled interview).
- Any other reason for which the principal investigator believes the participant should be withdrawn.

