4.0 Eligibility Criteria

4.1 Patient Inclusion Criteria:

- Patient is at least 3 weeks post-diagnosis of unresectable stage III or stage IV gastrointestinal cancer (i.e., anal, colon, esophageal, gallbladder, liver, pancreatic, rectal, small intestine, or stomach cancer) and is receiving care at the Indiana University Simon Cancer Center or Eskenazi Health.
- Patient is at least 18 years of age.
- Patient has adequate English fluency for study participation.
- Patient is willing to participate in this study.
- Patient has moderate to severe fatigue interference (i.e., mean score ≥ 2.5 on the Fatigue Interference subscale of the Fatigue Symptom Inventory)^{36, 37}
- Patient has an eligible, consenting family caregiver (see criteria below)

4.2 Patient Exclusion Criteria:

- Patient makes 3 or more errors on a validated 6-item cognitive screener⁴⁷ or exhibits significant psychiatric or cognitive impairment (dementia/delirium, intellectual disability, active psychosis) that in the judgment of the investigators would preclude providing informed consent and study participation.
- Patient Generated Subjective Global Assessment (PG-SGA; the patient-reported version of the Eastern Cooperative Oncology Group score) >2 .⁴⁸
- Patient is receiving hospice care at screening.
- Patient does not have working phone service.
- Patient has hearing impairment that precludes participation.

Note: Patients who enroll in hospice during the trial will have the option of continuing trial participation.

4.3 Caregiver Inclusion Criteria:

- Family caregiver identified by an unresectable stage III or stage IV gastrointestinal cancer patient who meets the eligibility criteria.

- Caregiver lives with the patient or has visited the patient in-person at least twice a week for the past month.
- Caregiver is at least 18 years of age.
- Caregiver has adequate English fluency for study participation.
- Caregiver is willing to participate in this study.
- Caregiver has moderate to severe caregiving burden, defined as a score ≥ 6 on the 6-item Zarit Burden Interview³⁹ or a T-score ≥ 60 (at least one standard deviation above the population mean) on the 4-item PROMIS anxiety or depression measures.⁴⁹

4.4 Caregiver Exclusion Criteria:

- Caregiver exhibits significant psychiatric or cognitive impairment (dementia/delirium, retardation, active psychosis) that in the judgment of the investigators would preclude providing informed consent and study participation.

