Target date = approximately 2 weeks after the last intervention session. Assessments can be completed as early as 7 days prior to this target follow-up date or as late as 14 days following the target follow-up date.	(5) Patients and caregivers will complete a 30-minute assessment over the phone (see "interview procedures" below). Assessments will be administered by a trained research assistant or a trained doctoral student in clinical psychology who are blinded to the intervention arm.
Target date = within 2 weeks of the 2-week post-intervention assessment. The qualitative interview can be completed as early as the same day as the 2-week follow-up or as late as 21 days after the 2-week follow-up.	(6) Patients and caregivers in the ACT condition will complete a 30-minute qualitative phone interview on intervention acceptability. The interview will be administered by a trained doctoral student in clinical psychology.
Target date = approximately 3 months after the last intervention session. Assessments can be completed as early as 7 days prior to this target follow-up date or as late as 21 days following the target follow-up date.	(7) Patients and caregivers will complete a 25- or 20-minute assessment over the phone, respectively. Assessments will be administered by a trained research assistant or a trained doctoral student in clinical psychology who are blinded to the intervention arm.

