Advanced patients and caregivers ($N = 50$ dyads) who are eligible and provide informed consent will complete individual phone assessments at baseline and approximately 2 weeks and 3 months following the final intervention session (see Table 1 in section 5.0 above for allowable assessment windows). The baseline assessment takes about 30 minutes for patients and 25 minutes for caregivers. Each follow-up assessment takes about 25 minutes for patients and 20 minutes for caregivers. Interviewers will be blind to study condition. Assessments will include questions regarding demographics, medical history, and primary and secondary outcomes. Participants will be provided with copies of response options via email or postal mail to facilitate survey completion (see Appendix E). Patients and caregivers in the ACT condition will also be invited to complete a 30-minute individual qualitative interview about intervention acceptability within approximately two weeks of the 2-week follow-up assessment. Each participant will receive \$40 in Target gift cards via postal mail for each completed assessment (baseline and 2-week and 3-month follow-ups) for a possible total of \$120 in gift cards (\$160 in gift cards for ACT participants only) for their time. There is no cost to study participants. If we cannot reach

a participant for an interview or phone session after several attempts, we will mail them a letter asking them to contact the study team (Appendix C). Table 2 below outlines the assessment schedule at baseline and the two follow-ups.

Table 2. Quantitative Measures						
Domain	Measure	# Items	Baseline	2-week follow-up	3-month follow-up	Administered to Patients (P) or Caregivers (C)
Sociodemographics	Sociodemographics	7-8	X			P, C
Medical comorbidity	Checklist of 8-9 conditions	8-9	X			P, C
Functional status	Patient-reported ECOG	1	X	X	X	P
Cancer information (e.g., date of diagnosis, cancer treatments)	Chart review	n/a	X	X	X	N/A
Intervention acceptability	Intervention acceptability scale	6		X		P, C
Primary patient outcome: fatigue interference	Fatigue interference subscale of FSI	7	X	X	X	P
Primary caregiver outcome: caregiving burden	12-item short-form of Zarit Burden Interview	12	X	X	X	C
Secondary outcomes:						
• Sleep interference	PROMIS short-form sleep-related impairment measure	8	X	X	X	P
• Engagement in daily activities	PROMIS short-form measure of ability to participate in social roles and activities	6	X	X	X	P, C

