Baseline and follow-up measures: Patients and caregivers will complete a baseline assessment and two follow-up assessments using the measures described below (see Appendices F-I). The baseline assessment takes about 30 minutes for patients and 25 minutes for caregivers. Each follow-up assessment takes about 25 minutes for patients and 20 minutes for caregivers. All self-report measures have strong evidence of reliability and validity. PROMIS measures were tested with over 21,000 people, including cancer patients.⁵⁵⁻⁵⁸ Validated non-PROMIS measures will be used for constructs that PROMIS measures do not currently assess (e.g., fatigue interference). Patients and caregivers in the ACT condition will also complete a 30-minute qualitative interview on intervention acceptability (see Appendix J). Baseline and follow-up assessments and qualitative interviews will be audio-recorded so that the PI or a trained member of the study team may audit them for adherence to the study protocol. [name], a qualitative methodologist, will randomly review at least 20% of qualitative interviews.

Demographic/medical factors. At baseline, patients and caregivers will report standard demographics (i.e., age, gender, race/ethnicity, marital status, education, income, employment status) and chronic medical conditions.^{59, 60} Caregivers will also report their relationship to the patient. Patients' cancer information will be collected via chart review (Appendix S).

Feasibility and acceptability data. Feasibility will be assessed by accrual rates, attrition, and adherence. At the 2-week follow-up, acceptability will be assessed with helpfulness ratings on a scale from 1 (did not help at all) to 5 (extremely helpful) for number and length of sessions, topics, therapist, and telephone format.⁵⁴ The RA will be blind to study condition, as the questions apply to either condition. For ACT participants, acceptability will also be assessed within 2 weeks of the 2-week follow-up via a 30-minute qualitative phone interview on the perceived helpfulness and impact of ACT components (see Appendix J for detailed interview guide). Qualitative interviews will be conducted with patients and caregivers separately. A doctoral student in clinical psychology with qualitative interviewing experience will conduct the interviews.

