Primary outcomes. For patients, fatigue interference will be assessed with the 7-item Fatigue Interference subscale of the FSI.^{36, 37} Items assess the extent to which fatigue in the past week interfered with activities, such as bathing, dressing, and housework, ability to concentrate,

enjoyment of life, and mood. For caregivers, caregiver burden will be assessed with the 12-item short form of the Zarit Burden Interview,^{38, 39} which evaluates personal strain and role strain due to caregiving.

Secondary outcomes. 1) Patient sleep interference will be assessed using the 8-item PROMIS sleep-related impairment measure,^{40, 41} which evaluates the perceived interference of sleep problems with activities, mood, and cognition. 2) Patient and caregiver engagement in daily activities will be assessed with the 8-item PROMIS measure of ability to participate in social roles and activities.⁴² The items, which are reverse-coded, measure difficulty engaging in social and recreational activities as well as usual work (including housework). 3) Patient and caregiver progress in value-based living will be measured by the 5-item Value Progress subscale of the Valuing Questionnaire.⁴³ This subscale assesses progress in living consistently with personal values. 4) Patient and caregiver psychological flexibility will be evaluated with the 7-item Acceptance and Action Questionnaire-II (AAQ-II).⁴⁴ 5) Patient QoL will be assessed with the 15-item McGill Quality of Life Questionnaire-Revised, which was designed for patients with life-threatening illnesses and evaluates physical, existential, and social well-being.⁴⁵ Caregiver QoL will be assessed with the 10-item PROMIS measure of global health, including physical, mental, and social well-being.⁴⁶

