11.0 Statistical Considerations

Aim 1. Feasibility and acceptability will be evaluated via descriptive statistics for accrual, attrition, and adherence as well as Likert-scale items assessing intervention helpfulness. We will judge this trial as feasible if: 1) $\geq 60\%$ of screened eligible dyads enroll in the study;²¹ and 2) $\geq 70\%$ of enrolled dyads complete 5-6 intervention sessions and all assessments. We will judge this trial as acceptable if $\geq 70\%$ of dyads rate ACT as moderately to extremely helpful (i.e., an average score ≥ 4 on 1 to 5 Likert scale items).

To analyze qualitative data on ACT's acceptability, we will use an immersion/crystallization approach.⁸⁰ Research questions guiding the analysis pertain to the perceived helpfulness of ACT components and their impact on functioning and well-being. Interviews will first be transcribed by a trained research assistant. Analysis of the interview data will consist of two phases: open and focused coding.^{80, 81} In the open coding phase, the analysts (Drs. [name], [name], and a Ph.D. student in clinical psychology) will independently label each line of data to reflect meanings or themes emerging from the text. This is done iteratively, combining, adding, or eliminating themes, until analysts agree on a set of emergent thematic categories (codes). In focused coding, codes derived in open coding are independently applied to all transcripts. Special attention will be paid to negative cases (i.e., data that may call initial observations or interpretations into question).⁸² Transcripts will be divided evenly among analysts, with every fourth transcript coded in common to maintain consistency in coding over time. Analysts will meet bi-weekly to compare commonly-coded transcripts. Discrepancies will be resolved by consensus. Atlas-ti software will facilitate coding, and qualitative results will inform intervention refinement.

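### Section 10.0 ends a remaining dyad member's assessments, not only the sessions, when the partner is lost, so obtainable follow-up data go uncollected

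*Combined protocol and SAP*

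**What the plan says.** Section 10.0 lists the reasons for removing someone from the study. One covers a patient or caregiver who dies, cannot go on for medical reasons or chooses to stop: "then the other member of the dyad (patient or caregiver) will no longer be eligible to participate in this study". It sets no time limit and does not distinguish the sessions from the assessments. The bullet before it, on a caregiver who declines or proves ineligible, gives a reason for excluding the patient: "as we are interested in examining data from patient-caregiver dyads". The one provision for continuing is the note at the end of Section 4.2, "Patients who enroll in hospice during the trial will have the option of continuing trial participation". That note concerns the patient's own move to hospice, not a person whose partner has been lost.

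On measurement, Section 7.0 (Interview Procedures) says that patients and caregivers "will complete individual phone assessments at baseline and approximately 2 weeks and 3 months following the final intervention session". On acceptability it adds: "Qualitative interviews will be conducted with patients and caregivers separately". Four of the six sessions (1 and 4 to 6) are joint.

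On analysis, Section 11.0 (Aim 2) models patient fatigue interference and caregiver burden each in a single-role repeated-measures mixed model. Dyadic models are kept for outcomes that both roles report. The missing-data paragraph plans multiple imputation with 50 samples, a comparison of withdrawers on demographic and medical factors, and tracking of reasons for dropout.

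**The concern.** A randomised person who is willing to answer the phone is dropped because of something that happened to someone else. The triggers (death, illness, stopping) occur after randomisation and are plausibly related to fatigue and burden. The rule is wider than the dyadic format requires. No scheduled contact after session 6 is joint, yet a partner lost in that period still ends the other person's 3-month call.

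At stake are the Aim 2 effect sizes, which are meant to inform the larger trial, and the Aim 3 service-use analyses, which cover the whole study period. A member removed before the 2-week follow-up also gives no acceptability rating and, in the ACT arm, no qualitative interview.

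**Working it through.** **1. Does any passage soften the rule?** That assessments stop is an inference: the list is of removals from the study, and the remaining member loses eligibility for the study. No passage supports a narrower reading.

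**2. Which primary-outcome data are still obtainable?**

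| Who is lost | Outcome of the remaining member | Obtainable? |
|---|---|---|
| Caregiver, any reason | Patient fatigue interference | Yes |
| Patient, alive but out of the study | Caregiver burden | Yes |
| Patient, by death | Caregiver burden | No |

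The last row follows from Section 7.0 (Primary outcomes), which describes the burden scale as one "which evaluates personal strain and role strain due to caregiving". Other caregiver outcomes can be asked after a death, but they then also reflect bereavement.

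**3. Reproduce the plan's figure.** Inputs from Section 11.0 (Statistical power): 34 per role, two-sided 0.05, 80% power. Detectable d = (t at 0.975 + t at 0.80, both on n − 2 df) × √(4/n). At n = 34 this is (2.037 + 0.853) × 0.343 = 0.991, against the stated .99. It reproduces.

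**4. Cost of the rule.** Section 11.0 gives 15% attrition but does not say whether that is per dyad or per member; the equal counts for both roles fit per dyad. Assumptions: N = 50 dyads, independent losses at equal rates in both roles, and every remaining member agreeing to continue.

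- Per dyad: with the rule, 50 × 0.85 = 42.5 per role. The member rate p solves (1 − p)² = 0.85, so p = 0.078. Without the rule, 50 × 0.922 = 46.1. Cost: 46.1 − 42.5 = 3.6.
- Per member: without the rule, 50 × 0.85 = 42.5. With it, 50 × 0.85² = 36.1. Cost: 50 × 0.15 × 0.85 = 6.4.

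Because Aim 2 estimates effect sizes, the table also gives the 95% confidence half-width at d = 0, which is 1.96 × √(4/n).

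| 15% read as | n per role, with / without rule | Detectable d, with / without | Half-width, with / without |
|---|---|---|---|
| Per dyad | 42.5 / 46.1 | 0.88 / 0.84 | 0.60 / 0.58 |
| Per member | 36.1 / 42.5 | 0.96 / 0.88 | 0.65 / 0.60 |

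**5. Range.** If both members of a dyad are always lost together, the cost is 0. If they never are, it is 50 × 0.075 = 3.75 (per dyad) or 50 × 0.15 = 7.5 (per member). If patients are lost more often than caregivers, the cost falls mostly on caregivers.

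For burden, deaths must be taken out. If half of patient losses are deaths, the cost is 3.6 × 0.5 = 1.8 or 6.4 × 0.5 = 3.2; if all are, it is 0.

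The planned 34 per role is 85% of 40, not of 50; that mismatch is a separate matter. On a base of 40 the independent-loss costs would be 2.9 and 5.1. The 15% is stated for the 2-week assessment, so the 3-month loss cannot be sized from the document.

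**6. Feasibility criterion.** Section 11.0 (Aim 1) asks that at least 70% "of enrolled dyads complete 5-6 intervention sessions and all assessments". A dyad that has lost one member before the end of follow-up misses this with or without the rule, so the criterion is hardly touched.

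**The case against.** The rule has a plausible design basis. The intervention is dyadic, most sessions are joint, and outcomes reported by both roles are analysed with a covariance between partners. The stated interest in dyad data sits in the adjacent bullet. This explains why sessions may need both people. It does not explain why individual calls must stop, least of all for outcomes analysed in one role.

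The plan also has an answer to lost follow-up: 50 imputations, and a mixed model that uses baseline and any completed follow-up. That deserves credit, but both work from data already collected. They stand in for answers that a willing person could have given, where the loss is plausibly related to the outcome.

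Continued collection is not purely beneficial. Quality-of-life or activity scores from a bereaved caregiver mix grief with the intervention effect, and patient and caregiver results would rest on different sets of dyads. This stands, and the fix has to deal with it.

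The numbers are small, every range starts at 0, and on N = 50 each scenario leaves at least 35 per role, above the 34 planned. This also stands.

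A reader might infer that the rule biases the comparison between arms. Differential loss is possible, but nothing in the document shows it. A reader might also infer that the feasibility verdict is compromised; step 6 shows that the completion criterion is not.

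**Conclusion.** The point holds as a cheap improvement. As written, Section 10.0 discards obtainable outcomes of willing randomised people, chiefly patients whose caregiver is lost and caregivers of a living patient who has left the study. Burden after the patient's death is not among the recoverable data.

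Under the assumptions in step 4, the cost is about 3.6 or 6.4 people per role, depending on what the 15% refers to. It is nil if losses fully coincide and smaller for burden to the extent that patient losses are deaths. Precision changes little. The stronger reason to act is that the missingness is avoidable and tied to illness, death or stopping.

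Aim 2 and Aim 3 carry most of the effect. The primary objective is touched only through missing acceptability ratings and ACT interviews from members removed before the 2-week follow-up.

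**What to change.** Amend Section 10.0, and the consent form if it repeats the rule, to separate leaving the sessions from leaving the assessments:

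- A remaining member who agrees completes the scheduled 2-week and 3-month phone assessments and is analysed as randomised.
- State the anchor date when sessions end early. Table 1 counts follow-up from the last session ("Target date = approximately 3 months after the last intervention session"), which is undefined in practice for a dyad that stops part-way.
- Caregiver burden is neither asked nor imputed after the patient's death.
- Other caregiver scores collected after bereavement are flagged and reported separately, with the Aim 2 effect sizes shown with and without them.

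Whether sessions continue for the remaining member is left to the sponsor.

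The cost is one amendment, a few extra calls and gift cards handled by existing staff, and care in contacting bereaved participants.
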